2.4 Correlative Studies Background-- Not applicable

3. PARTICIPANT SELECTION

Laboratory tests required for eligibility must be completed within 14 days prior to study entry. Other non-laboratory tests must be performed within the timeframes described below.

3.1 Eligibility Criteria

Participants must meet the following criteria on screening examination to be eligible to participate in the study:

- 3.1.1 Participants must have undergone biopsy or attempted surgical resection and must have histologically confirmed medulloblastoma or pineoblastoma. Confirmation of pathology at the treating institution is preferred prior to beginning study treatment, but may be received two weeks after radiation start.
- 3.1.2 Participants may have had a gross total resection, sub-total resection or biopsy only.
- 3.1.3 For patients with no prior chemotherapy, treatment must start within 35 days of definitive surgery or as indicated if enrolled on therapeutic study.
- 3.1.4 Age ≥ 3 and ≤ 25 at the time of enrollment.
- 3.1.5 Life expectancy of greater than 3 months.
- 3.1.7 Radiation is known to be teratogenic, women of child-bearing potential must not be pregnant at the time of study entry. Women and men must agree to use adequate contraception (hormonal or barrier method of birth control; abstinence) prior to study entry and for the duration of study participation. Should a woman become pregnant or suspect she is pregnant while participating in this study, she should inform her treating physician immediately.
- 3.1.8 Signed informed consent document and assent when appropriate.

3.2 Exclusion Criteria

Participants who exhibit any of the following conditions at screening will not be eligible for admission into the study.

- 3.2.1 Patients with more than one previous chemotherapy regimen.
- 3.2.2 Patients with recurrent or progressive disease after one or more regimens of pre-radiation chemotherapy.
- 3.2.3 Patients with prior radiation therapy will be excluded.

- 3.2.4 Any major uncontrolled or poorly controlled intercurrent illness that would limit compliance with study requirements.
- 3.2.5 Pregnant women are excluded from this study because radiation is a teratogen and it is not safe to the fetus to treat a patient while pregnant.

3.3 Inclusion of Women, Minorities and Other Underrepresented Populations

We do not expect the inclusion and exclusion criteria to either over or under represent women, minorities, or underrepresented populations.

4. REGISTRATION PROCEDURES

4.1 General Guidelines for DF/HCC and DF/PCC Institutions

Institutions will register eligible participants in the Clinical Trials Management System (CTMS) OnCore. Registrations must occur prior to the initiation of protocol therapy. Any participant not registered to the protocol before protocol therapy begins will be considered ineligible and registration will be denied.

A member of the study team will confirm eligibility criteria and complete the protocol-specific eligibility checklist.

Following registration, participants may begin protocol treatment. Issues that would cause treatment delays should be discussed with the Principal Investigator. If a participant does not receive protocol therapy following registration, the participant's protocol status must be canceled. Registration cancellations must be made in OnCore as soon as possible.

4.2 Registration Process for DF/HCC and DF/PCC Institutions

DF/HCC Standard Operating Procedure for Human Subject Research Titled *Subject Protocol Registration* (SOP #: REGIST-101) must be followed.

4.3 Registration Process for Other Participating Institutions

Eligible participants will be entered on study centrally by the MGH Coordinating Center. Please refer to Section 5.7 of the Data and Safety Monitoring Plan (attached as Appendix A) for details. If a participant does not receive protocol therapy following registration, the participant's registration on the study must be canceled. The Coordinating Center should be notified of cancellations as soon as possible.

5. TREATMENT PLAN: RADIATION THERAPY

All charged particle treatment will be given at the Francis H. Burr Proton Therapy Center or MD Anderson Proton Therapy Center. Film or digital images will be taken prior to each treatment in accordance with the proton center's standard practice for all patients. These

images are used to verify the position of the patient and the aperture. These images are permanently stored electronically for each patient. Treatment may start any day of the week but preferably Monday through Thursday. Expected toxicities and potential risks as well as dose modifications are described in Section 6 (Expected Toxicities and Dosing Delays/Dose Modifications). Patients with MB will be stratified into standard and high risk for treatment purposes. Physicians are strongly encouraged to enroll patients onto other active protocols. Children's Oncology Group (COG) has specifically designed their protocols to allow for proton radiation which will therefore not preclude co-enrollment.

Documentation of chemotherapy given should be submitted. In order to assess the causes of any possible acute or long term side effects, the total platinum dose given to the patient should be tracked. The cumulative platinum dose, number of cycles, and any dose reductions should be recorded.

5.1 Pre-Treatment Criteria

5.1.1 Baseline Staging Requirements:

- MRI scan with contrast enhancement (with gadolinium) of the entire spinal axis (preferably pre-op)
- Pre-operative MRI scan or CT scan of the brain.
- Post-operative MRI of the brain (within 21 days of surgery, preferably within 72 hours of surgery; intra-operative MRI is allowed).
- CSF sampling for cytology if the patient appears to have M0 disease. CSF sampling is not required for patients with gross M2 or M3 disease by imaging (leptomeningeal spread of disease in the brain or the spine). CSF sampling can be completed any time prior to the start of protocol therapy. If sampling for M0 disease performed less than 10 days after surgery is positive, it should be repeated. CSF sampling must be completed no later than ten days after the start of radiation.

5.1.2 Additional Baseline Assessments:

- Endocrine evaluation to be completed no later than 2 months after the start of radiation. To include TSH, Free T4, Cortisol, IGF-1 and IGF-BP3, LH, FSH, estradiol (females), testosterone (males) (am levels preferred), Tanner Stage assessed by physical exam, bone age (plain film of the wrist), and body proportion measurements. Bone age, Tanner Stage assessment, and body proportion measurements collected will be at the discretion of the study endocrinologist. Recommended measurements include sitting height (sitting height preferred, but pubic symphysis to floor acceptable), standing height, leg span, and arm span.
- Audiogram, to be completed no later than 2 months after the start of radiation.

- Neurocognitive evaluation, as detailed in Section 9.2.3, to be completed no later than 9 months after the start of radiation

5.2 Radiation Planning Guidelines

5.2.1 Patient Set-up and Immobilization

Patient set-up and immobilization must be determined prior to planning CT scan and may be either prone or supine. For CSI, patient will be positioned in accordance with the treating institution's accepted method of doing so. Head will be positioned such that the spinal cord is as straight as possible. Children unable to cooperate and remain properly immobilized should be sedated or anesthetized for set-up reliability on a day-to-day basis. A nurse anesthetist or anesthesiologist will be supervising and administrating sedation. Sedated patients should be under constant surveillance during treatments with cameras, telemetry, and other devices.

5.2.2 CT Simulation

The patient will have a planning CT scan while in the treatment position and properly immobilized. Physicians are encouraged to use available MRI scans to aid in target and normal tissue delineation. Electronic copies of MRI scans are usually available and can often be registered with planning CT scans to help delineate structures.

5.2.3 Target and Normal Structure Delineation

The following structures will be outlined on planning CT scans. It is recommended that the radiation oncologist outline the GTV. Cumulative dose volume histogram analysis will be completed for structures listed below:

- GTVp and surgical bed (see below for guidelines definitions)
- CTV1 and CTV2 (+/- CTV x...)
- Right and left cochlea
- Lenses
- Optic chiasm
- Pituitary gland
- Hypothalamus
- Esophagus
- Temporal lobes
- Whole brain

ICRU 50 and ICRU 78 [37] recommended terminology will be used to define radiation treatment parameters.

CTV1: Cranial-Spinal Treatment:

CTV1 shall be defined as the cranial spinal portion of the treatment and will include the entire cranial contents including cribriform plate and the thecal sac surrounding the spinal cord and nerve roots. Care should be taken to look at the sagittal spine MRI to define

where the thecal sac ends and an additional margin of 1-2 cm should be added to ensure coverage. When imaging is degraded or incomplete, coverage should extend to S4. The treating physician should use their judgment about whether the target will also include the vertebral body or only the thecal sac. However, in patients that have a significant amount of growth to do it is recommended that the whole vertebral body (or nearly so) be covered so as to avoid uneven growth of the vertebral body resulting in spinal scoliosis.

CTV2: Posterior Fossa or Involved Field Boost:

The GTVp is defined as any post-operative residual tumor seen on MRI or CT scan in addition to the collapsed resection cavity of the primary lesion.

The CTV2 is defined as 1-1.5 cm anatomically constrained margin around the GTVp and any other sites the treating physician judges to be at high risk for microscopically residual disease. Or, if the tumor is arising in the posterior fossa, the entire posterior fossa may be boosted. This is up to the COG protocol or physician discretion after consultation with the patient (if appropriate) or/and their guardians.

Metastases boosts:

Guidelines for boosting metastatic disease (ie M1, M2 or M3) will be in accordance with the COG guidelines and institutional practice, but are briefly outlined below.

CTV 3, 4, 5, etc:

The boosts for the gross metastatic deposits will be targeted with a 5-10 mm margin of CTV and include any other area the treating physician feels is at high risk for local recurrence.

Planning Target Volumes (PTV):

An additional margin for set up uncertainty and motion will be applied according to each institution's regular practices.

The *irradiated volume* includes normal tissue, which receives a clinically significant dose with respect to normal tissue effects.

5.2.4 Dosimetry Planning

Cranial spinal planning will be according to each institution's standard protocol for this technique and will include moving junctions of matched fields for safety.

5.2.5 Dose Specification and Schedule

Physicians are encouraged to enroll patients onto other active protocols (e.g. testing chemotherapy regimens). The radiation dose and fractionation schedule in these cases is in accordance with the co-existing protocol. Patients will usually be treated once per day. Doses will be prescribed such that 95% of the CTV is covered by 100% of the prescription dose. Dose will be reported in GyRBE (where 1 GyRBE = proton dose Gy x

RBE, RBE = 1.1). A RBE of 1.1 has been selected for protons and is based on RBE determinations in animal and cell culture systems [43,44].

Cumulative dose volume histograms using nominal dose distribution will be generated for all structures listed in 5.2.3.

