Conductive hearing loss due to serous otitis media is a well-known acute reaction to RT and stems from mucositis causing blockage of Eustachian tube with transudation of serous fluid. Patients are at increased risk at doses > 40 Gy. Most cases resolve spontaneously.

Sensorineural hearing loss (SNHL) caused by damage to the cochlea and auditory nerve is a late complication from RT and can result in permanent hearing loss. While high doses of radiation are needed in the absence of chemotherapy to invoke SNHL [5-6], it can occur with lower radiation doses when ototoxic platinum chemotherapy agents are used. Evidence exists suggesting a dose response. Schoenthlaer et al reviewed 25 patients treated with high dose proton beam RT for base of skull tumors. Six patients developed decreased hearing acuity as a late complication. All patients with hearing loss received more than 60 cobalt gray equivalent (CGE) to at least 50% of the cochlea and auditory nerve [5]. In contradistinction, no patient receiving less than 60 CGE had hearing loss. Grai et al observed a higher incidence of severe SNHL in nasopharyngeal carcinoma patients receiving > 50 Gy to the inner ear compared to < 50 Gy [6]. Thibadoux et al found no hearing deficits in children receiving prophylactic cranial irradiation for acute lymphocytic leukemia [7]. Patients received 24 Gy in 2 Gy fractions. Hua et al studied the effect of cochlear dose on sensorineural hearing loss in children with brain tumors treated with conformal radiation therapy and no ototoxic chemotherapy. They found that there is significant correlation between radiation dose and the incidence of sensorineural hearing loss in children. Children with a cochlear mean dose of 30 Gy or less had a low incidence of hearing loss, while there was an increased risk at greater than 40-45 Gy [8].

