5.2.8 Quality Assurance and Rapid Review of Treatment Plans

To ensure protocol compliance, the treatment plans for the first three patients treated at each site will be reviewed by the Principal Investigator and Participating Site's PI. As described in Section 12.1.3, below, plans will be submitted to the Advance Technology QA Center at Washington University, St Louis (ATC) for this protocol. The plans will be sent to the ATC upon approval by the treating physician, and the PI and/or Participating Site PI will review and confirm protocol compliance within three working days of the start of treatment.

5.2.9 Beam Verification:

Digitally reconstructed radiography (DRR) will be done for treatment planning and verification and will be performed daily during treatment.

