5.2.13 Treatment Delay

To avoid treatment delays resulting from the machine being down, photon or electron (if appropriate) beam radiation can be administered. The maximum dose for both the posterior fossa and spine will be 20% of the prescribed dose (e.g. 20% of the spine at 36 Gy would be a maximum of 4 spine treatments or 7.2 Gy). Delay in the start of CSI proton therapy shall not exceed 2 weeks in M0 patients and 1 week in M+ patients.

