14.4 Analysis of Endpoints

Progression-free survival is measured from the start of radiation therapy to the date of documented disease progression or death in the absence of progression. Patients who have not progressed or died will be censored at the time of last follow up. Progression-free survival will be estimated by the Kaplan-Meier method. Acute effects will be summarized according to specific events with exact 95% confidence intervals for binary data. The incidence of late complications will be based on actuarial estimates, primarily at 3 years. Patients who die, progress, or are lost to follow up prior to 3 years will be censored. Other factors which may influence late complications will be explored in multivariate models, including gender, age, radiation dose to the posterior fossa, dose volume histogram of the normal tissue as well as drugs, dosages and sequencing of the chemotherapy regimen. In addition, we shall control for pre-existing hearing deficits in the analysis of ototoxicity, while methotrexate usage will be of interest in the analysis of neurocognitive functioning among high-risk patients. Multivariate analyses will be primarily exploratory due to the modest patient numbers in each risk group.

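### The DVHs used in the late-effect models rest on an undefined nominal dose, and no available section adds the permitted photon or electron fractions

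*Combined protocol and SAP*

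**What the plan says.** Section 5.2.3 lists the structures to be outlined, including "Right and left cochlea". Section 5.2.5 then sets the dose basis: "Cumulative dose volume histograms using nominal dose distribution will be generated for all structures listed in 5.2.3". Nominal is not defined. The same section reports dose in GyRBE, defined as proton dose times 1.1, and gives no rule for adding photon dose.

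Section 5.2.8 places transfer to the imaging archive at plan approval: "The plans will be sent to the ATC upon approval by the treating physician". Section 12.1.3 says that the archive holds each subject's data for analysis by investigators, and gives no timing.

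Section 5.2.13 allows a change of modality during treatment: "To avoid treatment delays resulting from the machine being down, photon or electron (if appropriate) beam radiation can be administered". Its limit reads "The maximum dose for both the posterior fossa and spine will be 20% of the prescribed dose". Section 6.3 repeats the allowance for photons. Section 5.2.14 allows photons or electrons for emergent treatment when no proton slot is available, with a differently worded posterior fossa limit.

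Section 14.4 lists the "dose volume histogram of the normal tissue" among the factors to be explored in multivariate models of late complications, and calls those models primarily exploratory.

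**The concern.** A covariate meant to explain late damage should be the dose that the child received. The plan names a nominal distribution, sends plans to the archive at approval, and allows later fractions in another modality. No available section calls for a summed or updated plan. By contrast, Section 5 asks for cumulative platinum dose, cycles and reductions so that the causes of side effects can be assessed. For delivered radiation, the comparable record is the length of and reason for treatment breaks (Section 9.1).

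Any omission would not be random noise around the true dose. Table 1 gives the cochlea far more dose per prescribed Gy with photons than with protons, so the error runs one way and falls only on the children who had photons. Their hearing loss would be attributed to a lower cochlear dose than they received. Table 1 shows the same direction for the pituitary gland (57.2% with protons against 80.1% and 91.1% with photons) and for non-posterior-fossa brain (26.1% against 47.1% and 40.6%), so the endocrine and neurocognitive models are exposed as well.

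**Working it through.** **The plan's own figure.** Section 5.2.13 gives the example "20% of the spine at 36 Gy would be a maximum of 4 spine treatments or 7.2 Gy". 0.20 × 36 = 7.2 Gy, and 7.2 / 4 = 1.8 Gy per fraction. It reproduces, but it is a spine-field example and not a cochlear dose.

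**Inputs from Table 1 (posterior fossa field, mean cochlear dose as % of prescription).** Lateral opposed photons 102.3; conformal photons 55.0; conformal protons 11.7. Ratios to protons: 55.0 / 11.7 = 4.7 and 102.3 / 11.7 = 8.7.

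**Assumptions.** The trial's boost dose is not stated. I use 18 to 20 Gy (a boost reported for a cited study in Section 2.3), 30.6 Gy (an assumed 54 Gy total minus 23.4 Gy craniospinal dose), and the 54 Gy total itself. Photon Gy and GyRBE are added one for one. The DVH is taken to show the all-proton plan. Table 1 gives nothing for electrons.

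**Formula.** Understatement = 0.20 × D × (photon share − proton share). The differences are 0.550 − 0.117 = 0.433 and 1.023 − 0.117 = 0.906.

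| Dose D to which the cap applies | 0.20 × D | Conformal (× 0.433) | Lateral opposed (× 0.906) |
|---|---|---|---|
| 18 Gy boost | 3.6 Gy | 1.6 Gy | 3.3 Gy |
| 20 Gy boost | 4.0 Gy | 1.7 Gy | 3.6 Gy |
| 30.6 Gy boost | 6.12 Gy | 2.6 Gy | 5.5 Gy |
| 54 Gy total, all given in the boost | 10.8 Gy | 4.7 Gy | 9.8 Gy |

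One 1.8 Gy photon fraction gives 0.8 or 1.6 Gy. No photon fractions gives 0. For scale, an all-proton boost of 18 to 30.6 Gy gives the cochlea 0.117 × D = 2.1 to 3.6 Gy.

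**Against the cited risk level.** Section 2.3 reports: "Children with a cochlear mean dose of 30 Gy or less had a low incidence of hearing loss". That study had no ototoxic chemotherapy. If the cochlea receives the full craniospinal dose (an assumption), the recorded dose is 23.4 + 0.117 × 30.6 = 27.0 GyRBE. Adding the understatement gives 29.6 (conformal) or 32.5 (lateral opposed). Only the second passes 30.

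**Effect on the models.** I simulated a logistic model of hearing loss on cochlear dose, fitted once to delivered and once to nominal dose. Assumptions, none from the documents: slope 0.10 per Gy, planned dose mean 30 and SD 5 Gy, risk 14% at 25 Gy, 5 to 10% of children affected, and z scaled to 68 children (48 + 20).

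- Understatement 1.6 to 5.5 Gy: z for the slope falls by at most 0.1, and modelled risk at 25 Gy rises by less than 1 percentage point.
- Understatement 9.8 Gy: z falls from 1.8–1.9 to 1.6, and modelled risk rises from 14% to 15–16%.

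The plan analyses the risk groups separately, so actual z values would be lower still.

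**Primary rules.** Exact binomial values for the two rules in Section 14.1 are 0.132 error and 0.772 power (7 or fewer of 20), and 0.081 error and 0.800 power (14 or fewer of 48). They match the stated 13%, 77%, 8% and 80%, and no DVH enters them.

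**The case against.** The best defence is that the text is silent rather than wrong. Nominal may mean the distribution without range and set-up uncertainty, which would not exclude a photon component. The approval timing in Section 5.2.8 belongs to a compliance review, while Section 12.1.3 sets no timing and does not restrict the archive to the first plan. The data submission schedule is in Appendix A, which is not in the text available, so capture of delivered dose there cannot be ruled out. All of this stands. A reader might infer that photon fractions are definitely omitted, but the documents do not say so. What remains is that the dose basis of an analysis covariate is undefined.

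A reader might also infer a much larger error, for example 30.6 × 0.906 = 27.7 Gy if the whole boost were given with lateral opposed photons. That needs one reading of Section 5.2.14, an assumed boost dose, and an undelivered proton boost plan left on record. A boost planned with photons would have its own plan to approve and archive. Even the 4.7 to 9.8 Gy range needs six 1.8 Gy photon fractions (10.8 / 1.8), all in the boost, so it is an upper range.

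Courses stopped early under Section 5.4 do not support an understatement: there the nominal plan overstates dose. The claim that children cross a risk level rests on full craniospinal dose to the cochlea, whereas Section 2.3 reports less inner-ear dose with proton cranial fields.

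**Conclusion.** The point holds as a gap in specification with a known direction of error. Read as the approved proton plan, the nominal DVH understates mean cochlear dose in children given posterior fossa photon fractions: by about 1.6 to 2.6 Gy with conformal photons or 3.3 to 5.5 Gy with lateral opposed photons when the cap applies to the boost, and by no more than 4.7 to 9.8 Gy on the widest reading of the 20% cap. These sizes rest on Table 1, on assumed boost and total doses, and on use of the full cap.

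The number of affected children is not stated. Only the exploratory models of Section 14.4 are touched. A reader might infer that the trial's hearing-loss conclusion is biased; it is not, because the decision rules and actuarial estimates do not use DVHs. The change is still worth making, because these models are where the plan relates dose to late effects, and in groups of about 48 and 20 a few misrecorded children can carry weight.

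**What to change.** In Sections 5.2.5 and 14.4, define nominal and state that the DVHs used in late-effect models are of delivered dose: a plan sum, in a common unit, of the proton fractions given plus any photon or electron fractions. It should be made at the end of radiation and sent to the archive. State how photon and electron dose is combined with GyRBE, and record such fractions by site, technique and dose. Keep the nominal DVH for plan review. If a sum cannot be made for some children, specify a sensitivity analysis without them.

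The cost is protocol wording and one plan summation for each child with photon or electron fractions or an incomplete course. Children treated exactly as planned need nothing.

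Separately, Sections 5.2.13 and 5.2.14 differ on the photon limit for the posterior fossa. The sponsor must reconcile them.
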